## 3.0 HYPOTHESIS AND OBJECTIVES

### 3.1 Hypothesis

- Early enteral dextrose decreases inflammation, increases incretin hormones, prevents hyperglycemia, and preserves a healthy gut microbiome in critically ill septic patients

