#### 4.1.2 Hyperglycemia and inflammation in sepsis

Approximately 40% of patients in the intensive care unit develop hyperglycemia, and, of those, one third do not have pre-existing diabetes. The development of hyperglycemia in previously non-diabetic patients with sepsis (referred to as stress hyperglycemia) is associated with increased organ dysfunction and mortality. Stress hyperglycemia shares many characteristics with diabetes mellitus type 2: disrupted glucose homeostasis, impaired insulin sensitivity, inflammation, and counter-regulatory hormone imbalance. Once hyperglycemia develops, it further increases production of pro-inflammatory cytokines, suppresses neutrophil activity, and increases leukocyte adhesion and migration. While

initial clinical trials in critically ill patients demonstrated mortality benefits with tight glycemic control using intravenous insulin, subsequent trials have failed to replicate the same benefits with the use of insulin alone. Better understanding of the mechanisms contributing to hyperglycemia during sepsis and newer strategies to prevent its development, as proposed in our study, rather than respond once hyperglycemia has occurred are needed to improve patient outcomes.

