#### 5.1.1 Inclusion criteria

1. Adults aged 18 years and older admitted to an ICU at UPMC Presbyterian, UPMC Montefiore, UPMC Shadyside, or UPMC McKeesport.
2. New presentation of sepsis characterized by a confirmed or suspected infection, with an acute increase from baseline in a modified Sepsis-Related Organ Failure Assessment (SOFA) score of greater than or equal to 2 points (Appendix 11.1). If baseline values are unknown, baseline SOFA score of 0 will be assumed.
3. Available enteral access defined by: (1) an existing nasogastric or orogastric tube, (2) plans to place a nasogastric or orogastric tube, or (3) an existing percutaneous endoscopic gastrostomy (PEG) tube.
4. Less than 48 hours since meeting criteria for sepsis.
5. Expected to stay at least 24 hours in the ICU.

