#### 5.1.2 Exclusion Criteria

1. Pre-existing continuous enteral tube feed use prior to study entry.
2. Diabetic ketoacidosis or diabetic hyperosmolar hyperglycemic syndrome.
3. Previously enrolled in this study within the same hospital admission.
4. ICU physician request to exclude patient based on clinical assessment or contraindication to enteral feeding.

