### **5.2.3 Baseline evaluation and randomization:**

If pre-entry evaluation is acceptable, the participant will be enrolled in the study and undergo baseline testing included in Section 5.4.3. At that point, the participants will be randomized to interventional and placebo control arms. Enrollment into interventional and placebo arms will be stratified at one level by the presence or absence of pre-existing self-reported diabetes mellitus utilizing separate randomization tables. The University of Pittsburgh Medical Center Investigational Drug Service (UPMC-IDS) will be responsible for randomization, blinding, and providing the study infusion at the bedside to the clinical team.

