### **5.4.3 Baseline testing and randomization**

- Baseline clinical variable recording
- Pre-intervention capillary blood glucose measurement
- Initial research blood draw (up to 4 hours prior to the start of infusion)
- Aerodigestive tract samples for microbiome analyses (up to 4 hours prior to the start of infusion):
  - Oral swab
  - Tracheal aspirate (if the patient is on mechanical ventilation)
  - Gastric aspirate
- Colonic tract samples for microbiome analyses (up to 4 hours prior to the start of infusion)
  - Rectal swab
  - Stool sample (if available)

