### 9.2 Proposed statistical analysis

Primary statistical analysis comparing levels of pro-inflammatory cytokines will be determined by t-test (or non-parametric test if indicated) by intention-to-treat analysis. Differences in secondary continuous outcome variables between intervention and control groups will be determined by t-test or non-parametric test as appropriate. Differences in dichotomous secondary outcomes (development of

hyperglycemia, in-hospital mortality, etc.) will be determined by chi-squared analysis or Fisher's exact test as appropriate.

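### The glycemic comparisons in section 9.2 give no role to pre-infusion glucose or the diabetes stratum, although the aim is prevention and already hyperglycemic patients may enter

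*Combined protocol and SAP*

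**What the plan says.** The hypothesis in section 3.1 reads "Early enteral dextrose decreases inflammation, increases incretin hormones, prevents hyperglycemia, and preserves a healthy gut microbiome in critically ill septic patients". Section 4.1.2 explains the glycemic part as a need for "newer strategies to prevent its development, as proposed in our study, rather than respond once hyperglycemia has occurred". The same section gives the only frequency in the documents: "Approximately 40% of patients in the intensive care unit develop hyperglycemia, and, of those, one third do not have pre-existing diabetes".

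Entry is open to patients with raised glucose. The sole glucose-related exclusion in section 5.1.2 is "Diabetic ketoacidosis or diabetic hyperosmolar hyperglycemic syndrome". Section 5.1.1 sets the time window as "Less than 48 hours since meeting criteria for sepsis". Patients with diabetes are expected, because section 5.2.3 has randomisation "stratified at one level by the presence or absence of pre-existing self-reported diabetes mellitus". Section 5.4.3 schedules a "Pre-intervention capillary blood glucose measurement" for each participant.

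Section 9.2 assigns a t-test or non-parametric test to continuous secondary outcomes. It names development of hyperglycemia as the first example of a dichotomous one: "hyperglycemia, in-hospital mortality, etc.) will be determined by chi-squared analysis or Fisher's exact test as appropriate". It states no threshold, time window or denominator, no rule for participants hyperglycemic at entry, and no covariate. Intention-to-treat is named for the primary cytokine analysis; no population is stated for the secondary outcomes.

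**The concern.** Prevention can only be observed in someone who does not yet have the condition. A participant above the threshold before the infusion starts cannot newly develop hyperglycemia during it. Including such participants in the denominator pulls the two arms' rates together.

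The continuous glycemic comparisons have a related weakness. Glucose during a 24-hour infusion will plausibly depend on the glucose at its start and on diabetes. Both are recorded before treatment, and an unadjusted test leaves that variation in the error term. The randomisation is stratified by diabetes but the analysis ignores it.

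Section 4.2.1 says that improvement in inflammation and glycemic control would support a larger trial, so a diluted or imprecise glycemic estimate could mislead that decision.

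**Working it through.** **The plan's own figure.** There is none for hyperglycemia. Section 9.1 sizes the trial for IL-6 only and gives no standard deviation, so that calculation cannot be rebuilt from its stated inputs and does not bear on this point.

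**Inputs from the documents.** 36 per arm (Synopsis); alpha 0.05 (section 9.1; sides not stated, two-sided assumed).

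**Inputs assumed.** Share already hyperglycemic at entry, h = 20%, 30% or 40%, equal in both arms. New hyperglycemia among those at risk: pC = 40% on placebo and pT = 20% on dextrose.

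**Formulas.**
- Whole arms, prevalent cases counted as events: rates h + (1-h)pC and h + (1-h)pT.
- Whole arms, prevalent cases counted as non-events: rates (1-h)pC and (1-h)pT.
- At-risk only: rates pC and pT, with 36(1-h) per arm.

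Under either whole-arm coding the absolute difference is (1-h)(pC - pT). This part holds for any rates.

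**Example at h = 40%.**
- As events: 0.40 + 0.60 × 0.40 = 64% against 0.40 + 0.60 × 0.20 = 52%. Difference 12 points, relative risk 0.52/0.64 = 0.81.
- As non-events: 0.60 × 0.40 = 24% against 0.60 × 0.20 = 12%. Difference 12 points, relative risk 0.50.
- At-risk only: 40% against 20%. Difference 20 points, relative risk 0.50.

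**Power**, by exact enumeration of the pooled two-proportion (chi-squared) test:

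| h | Whole-arm difference | RR if events | Power, as events | Power, as non-events | At-risk per arm | Power, at-risk |
|---|---|---|---|---|---|---|
| 20% | 16 points | 0.69 | 26.7% | 35.4% | 29 | 37.7% |
| 30% | 14 points | 0.76 | 20.9% | 30.5% | 25 | 35.2% |
| 40% | 12 points | 0.81 | 17.2% | 26.2% | 22 | 29.8% |

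The at-risk analysis gains 11 to 14 points over event coding, but only about 2 to 5 over non-event coding, because the sample shrinks as the difference is restored.

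**Sensitivity to the assumed rates.**
- 50% against 20%, h = 20/30/40%: power 52/42/35% (events), 64/55/47% (non-events), 67/64/55% (at-risk).
- Taking the 40% of section 4.1.2 as the control-arm total, with h = 20%, incidence among those at risk is (40 - 20)/80 = 25%. If dextrose halves it to 12.5%, power is 15% (events), 22% (non-events) and 22% (at-risk).

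The power gain therefore depends on the rates and can vanish against non-event coding. The shrinkage of the absolute difference does not depend on them.

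**The case against.** The strongest reply is that section 9.2 never says whole arms are compared. It states no population for secondary outcomes, and development ordinarily means new onset, so the text is compatible with an at-risk analysis. That is fair. A reader might infer that the plan tests every participant, but this is read from silence. What stands is that the denominator and the handling of prevalent cases are unwritten, and could be settled after the data are seen.

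Other stronger readings also go too far:

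- **That about 40% are hyperglycemic at entry.** Section 4.1.2 gives the share of ICU patients who develop hyperglycemia, not the share who have it at the pre-infusion check.
- **That the trial cannot address glycemia.** The Synopsis and section 5.0 list glycemic control, variability, insulin dosing and hormone measures. The continuous measures do not require a participant to start below a threshold.
- **That dilution always biases the relative risk.** It does so under event coding only.
- **That participants high at entry are scored the same whatever the infusion does.** With no outcome definition this cannot be known; under an on-infusion definition they could fall below the threshold.
- **That chance imbalance in baseline hyperglycemia distorts the result.** Simple randomisation would give the between-arm difference a standard deviation of √(2h(1-h)/36), or 9 to 12 points for h of 20-40%. But randomisation is stratified by diabetes, and section 4.1.2 implies that two thirds of hyperglycemic ICU patients have it, so the figure overstates the imbalance. Chance imbalance is also already covered by the test's type I error.

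None of this supplies a reason to leave pre-infusion glucose and the stratum out of the glycemic comparisons.

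**Conclusion.** The point holds in a limited form. The hypothesis concerns prevention, already hyperglycemic patients are eligible, and section 9.2 plans unadjusted glycemic comparisons that ignore two baseline variables the trial already records. If development of hyperglycemia is tested across whole arms, the absolute difference shrinks by the factor (1-h): from 20 points to 16, 14 or 12 at h of 20%, 30% or 40%.

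The share at entry and the incidence rates are assumptions. Power for this comparison is low under every coding at 40% against 20%, so the at-risk denominator matters mainly because it makes the estimate match the hypothesis. The adjusted comparison of glucose in all randomised participants is the more useful change. Only secondary outcomes are affected; the primary IL-6 analysis is untouched.

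**What to change.** Amend section 9.2 before unblinding:

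1. **Continuous glucose.** Replace the unadjusted t-test with a comparison of on-infusion capillary glucose in all randomised participants, from a model adjusted for pre-infusion glucose and diabetes stratum. State how each participant's readings are summarised, because section 6.3.1 allows them to be more frequent than every six hours.
2. **Development of hyperglycemia.** Define it as a first reading above a threshold after infusion start, among participants below that threshold at the pre-infusion check. The sponsor should choose the threshold and record it in advance. Membership of this set is fixed before treatment, so the randomised comparison remains valid.

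The cost is wording, plus the choice of a threshold that the documents do not now contain. No new visit, sample or eligibility rule is needed. The downside is that the dichotomous comparison uses fewer participants: 72 × 0.60 to 72 × 0.80, or about 43 to 58 under the assumed range. Those already hyperglycemic still contribute to the continuous analysis.

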## **10.0 COSTS AND PAYMENTS**

### **10.1 Research study payments**

No research payment will be provided to participants or health care proxys in this study. When principal investigators are unavailable, study co-investigators will aide in screening, consenting, and enrolling participants and will be compensated \$20 for research activities. Principal investigators will not be reimbursed for research activities.

## 11.0 APPENDIX

### 11.1 Modified Sepsis-Related Organ Failure Assessment (SOFA) score

Adapted from Singer et al, modified to exclude assessments of liver function

Organ System	Score				
	0	1	2	3	4
Respiratory					
PaO 2 /FiO 2	Greater than or equal to 400	Less than 400 but greater than or equal to 300	Less than 300 but greater than or equal to 200	Less than 200 but greater than 100, with respiratory support	Less than 100, with respiratory support
Coagulation					
Platelet count	Greater than or equal to 150,000	Less than 150,000 but greater than or equal to 100,000	Less than 100,000 but greater than or equal to 50,000	Less than 50,000 but greater than or equal to 20,000	Less than 20,000
Cardiovascular					
Blood pressure	Mean arterial pressure greater than or equal to 70 mmHg	Mean arterial pressure less than 70 mmHg but not requiring vasopressor therapy	Requiring vasopressor therapy with dopamine less than 5 µg/kg/min for at least 1 hour or dobutamine at any dose	Requiring vasopressor therapy with either dopamine 5.1-15 µg/kg/min or epinephrine less than or equal to 0.1 µg/kg/min or norepinephrine 0.1 µg/kg/min for at least 1 hour	Requiring vasopressor therapy with either dopamine greater than 15 µg/kg/min or epinephrine greater than 0.1 µg/kg/min or norepinephrine 0.1 µg/kg/min for at least 1 hour
Central nervous system					
Glasgow Coma Scale	15	13-14	10-12	6-9	Less than 6
Renal					
Creatinine (mg/dL)	Less than 1.2	1.2-1.9	2.0-3.4	3.5-4.9	Greater than or equal to 5
Urine output (mL/day)				Less than 500 but greater than or equal to 200	Less than 200

**Note:** If the PaO2 is unavailable, this trial will allow for the substitution with the oxygen saturation (SpO2) for calculation of the SOFA score as per the table in Appendix 11.2.

## 11.2 Estimation of PaO2/FiO2 from SpO2/FiO2

Adapted from Huang et al

SpO 2	FiO 2														
	0.3	0.35	0.4	0.45	0.5	0.55	0.6	0.65	0.7	0.75	0.8	0.85	0.9	0.95	1
80%	141	127	111	98	89	81	74	68	63	59	55	52	49	47	44
81%	151	129	113	101	91	82	76	70	65	60	57	53	50	48	45
82%	155	132	116	103	93	84	77	71	66	62	58	55	52	49	46
83%	158	136	119	106	95	86	79	73	68	63	59	56	53	50	47
84%	162	139	122	108	97	89	81	75	70	65	61	57	54	51	49
85%	167	143	125	111	100	91	83	77	71	67	63	59	56	53	50
86%	171	147	129	114	103	94	86	79	73	69	64	61	57	54	51
87%	177	151	132	118	106	96	88	81	76	71	66	62	59	56	53
88%	182	156	137	121	109	99	91	84	78	73	68	64	61	58	55
89%	189	162	141	126	113	103	94	87	81	75	71	67	63	60	57
90%	196	168	147	130	117	107	98	90	84	78	73	69	65	62	59
91%	203	174	153	136	122	111	102	94	87	81	76	72	68	64	61
92%	213	182	159	142	128	116	106	98	91	85	80	75	71	67	64
93%	223	191	168	149	134	122	112	103	96	89	84	79	74	71	67
94%	236	202	177	157	142	129	118	109	101	94	89	83	79	75	71
95%	252	216	189	168	151	138	126	116	108	101	95	89	84	80	76
96%	273	234	205	182	164	149	136	126	117	109	102	96	91	86	82

### 11.3 Expected Adverse Effects of Sepsis

The following events are expected to occur with a reasonable frequency in the typical course of a critically ill patient with sepsis:

*Constitutional:* Fever, malaise, hypothermia, chills, rigors

*Cardiovascular:* Hypotension, arrhythmias (atrial fibrillation, atrial flutter, ventricular fibrillation, ventricular tachycardia), tachycardia, bradycardia, myocardial ischemia, syncope, shock

*Pulmonary:* Acute lung injury, dyspnea, hypoxemia, aspiration, atelectasis, mucus plugging, pneumothorax, pleural effusion, pulmonary embolism

*Gastrointestinal:* Nausea, vomiting, abdominal pain, paralytic ileus, ischemic bowel, gastritis, gastrointestinal bleeding, acute liver failure, pancreatitis

*Renal:* Dysuria, urinary retention, urinary frequency, incontinence, acute kidney injury, acute tubular necrosis, oliguria, acute interstitial nephritis, acidosis or alkalosis, hypokalemia or hyperkalemia, hyponatremia or hypernatremia

*Hematology:* Anemia, thrombocytopenia, abnormal coagulation, disseminated intravascular coagulation, hematoma, hemorrhage, venous thrombosis, pancytopenia

*Neurology:* Headache, confusion, delirium, hallucinations, agitation, anxiety, critical illness neuropathy

*Musculoskeletal:* Leg cramps, hemiparesis, quadriparesis, neuromuscular weakness, critical illness myopathy

*Dermatology:* Rash, bruising, cellulitis, Steven-Johnson syndrome, decubitus ulcer

## 13.0 PROTOCOL AMENDMENT LOG

- Version 1.0
  - Initial IRB submission: November 22, 2017.
  - Approved by Scientific Reviewer: January 4, 2018.
  - Changes requested by IRB: January 25, 2018.
  
- Version 2.0
  - Changes in this version
    - Mid-Intervention Assessment added in section 5.4.5.
    - Indications for Study Discontinuation updated in section 7.4 to include clinical evaluation that continuation of the intervention is unsafe due to elevated blood sugar, severe ileus, or severe abdominal pain or emesis as criteria for discontinuation.
    - Required Education in the Protection of Human Research Participants updated in section 7.7.1 to reflect that participants are at high risk for delirium and cognitive impairment at the time of consent.
  - Protocol updated February 8, 2018
  - Informed Consent forms updated February 18, 2018
  
- Version 3.0
  - Changes in this version
    - Exclusion Criteria (Section 5.1.2) updated to include ICU physician request to exclude patient based on contraindication to enteral feeding.
    - Study Exam and Procedures (Section 5.4) updated to include time frames for sample collection at pre-infusion, 24-hour, and day 7 time points.
    - Day 28 Testing and Procedures (Section 5.4.8) changed to Day 30 Testing and Procedures.
    - Baseline Evaluation and Randomization (Section 5.2.3) updated to reflect that enrollment into intervention and placebo arms will be stratified at one level by the presence or absence of pre-existing diabetes mellitus.
    - Research Payments (Section 10.1) updated to include payment for co-investigators for screening, consenting, and enrollment activities.
  
- Version 3.1
  - Changes in this version
    - Modified to reflect expansion of recruitment to the ICUs at UPMC Shadyside and UPMC McKeesport Hospitals in Section 5.1, Section 5.11, and Section 5.2.
